Calcium: Calcium carbonate will be supplied to all participants. Because hypocalcemia can occur with treatment of osteoporosis, it is important for adequate calcium to be available. All participants will be given supplemental calcium (1000 mg/day) to be taken as 500 mg tablets, one tablet twice daily. For individuals who are already taking calcium supplements or obtain sufficient calcium through their diet, the dosage of study calcium may be reduced in order not to exceed 1000 mg of exogenous calcium per day. We recognize that there may be a preference for calcium citrate due to the lack of interference with absorption with concomitant use of proton-pump inhibitors, but our experience has been that calcium carbonate is well tolerated and does provide adequate calcium intake in most clinical settings.

The FDA has issued a Safe to Proceed Letter on 08May2020 for IND#149486 for romosozumab and alendronate tablets.

IND holder: [name], PhD

The IND holder will comply with all sponsor requirements (reporting of SUSARs, annual reporting, etc).

PROCEDURES INVOLVED:

This is an open-label study of romosozumab 210 mg administered subcutaneously every month over a 12 month period followed by 12 months of oral weekly alendronate 70 mg treatment. Visits will occur as noted in the Study Procedures Flowsheet (Appendix A) and will take place at our research clinic in [name], at Northwestern University building at [name]

STU00212405

[name]. For participants who live more than 100 miles away and wish to receive monthly injections closer to their home, arrangements will be made with a local clinic to provide romosozumab injections for visits M7, M8, M9, M10, and M11.

Romosozumab will be administered by a licensed health care practitioner in the research clinic as outlined below or at a local clinic after month 6. At follow up visits during year 1, bone marker collection will occur prior to the romosozumab injections. During the Covid-19 pandemic, all Covid precautions will be followed per the Northwestern University policy and the research team's SOPs.

Childbearing potential will be determined based medical history and FSH results from the screening visit labs. Only subjects with childbearing potential will need documentation of a negative pregnancy test prior to imaging with DXA, CT, and/or injections of romosozumab.

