The local clinic will be responsible for study drug receipt, storage, administration, collection of vital signs during the visit, and documentation of visit details on source documents. The rest of the study visit, including adverse event follow up, concomitant medications, questionnaires will be performed by the study coordinator over the phone. For Month 9, participants will be asked about their study supplement compliance over the phone instead of performing a physical compliance check. For participants of childbearing potential, a negative urine pregnancy test will be done at home by the participant and results will be shared with the study coordinator prior to the subject receiving an injection. Participants will receive supplies to perform a urine pregnancy test at home and will be trained on the proper procedure at Month 6.

Visit 1: Screening

At this visit, after the study is explained and consent is obtained, a medical history will be recorded and the Spinal Cord Injury & Lifestyle Information (SCILI) will be collected. Vital signs (VS) and physical examination performed, EKG, and blood and urine obtained for screening testing (hematology, chemistry, endocrine parameters, pregnancy, vitamin D levels). A DXA scan will be performed and the Walking Index for Spinal Cord Injury II (WISCI) administered at this visit. If needed, screening procedures may be completed in multiple visits.

Those individuals with low vitamin D levels will be given an eight-week supply of 50,000 IU vitamin D to be taken once a week. Participants will be asked to return to for a blood draw to establish adequate levels of vitamin D prior to initiation of romosozumab.

Visit 2: Baseline (within up to 8 weeks after screening)

At this visit, inclusion/exclusion criteria will be checked. Urine pregnancy test will be done, if applicable. CT of the hip and knee will be performed and blood obtained for serum bone marker determination. Participants will then receive their first doses of IP and be dispensed vitamin D and calcium with instructions for their daily administration. WISCI will be performed and SCIM will be collected.

Visit 3 (Month 1)

VS will be obtained and AEs and concomitant medications recorded. Urine pregnancy test will be done, if applicable. IP will be administered by trained study staff. Participants will have

STU00212405

serum calcium and vitamin D levels checked at this visit. If the results are abnormal, these labs will be repeated at Visit 5 (Mo 3).

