Visit 4 (Month 2)

VS will be obtained and AEs and concomitant medications recorded. Urine pregnancy test will be done, if applicable. IP will be administered by trained study staff.

Visit 5 (Month 3)

VS will be obtained and AEs and concomitant medications recorded. Urine pregnancy test will be done, if applicable. IP will be administered: vitamin D and calcium will be provided. WISCI will be performed. DXA and CT of the knee will be performed and blood obtained for serum bone markers. If serum calcium and/or vitamin D levels were abnormal at Month 1, participants will be retested at this visit.

Visit 6 (Month 4) and Visit 7 (Month 5):

VS will be obtained and AEs and concomitant medications recorded. Urine pregnancy test will be done, if applicable. IP will be administered by trained study staff.

Visit 8 (Month 6):

VS will be obtained and AEs and concomitant medications recorded. DXA and CT of the hip and knee will be performed and blood obtained for serum bone markers. Urine pregnancy test will be done, if applicable. IP will be administered by trained study staff. Vitamin D and calcium will be provided. WISCI will be performed.

Visits 9-13 (Months 7-11):

VS will be obtained and AEs and concomitant medications recorded. Urine pregnancy test will be done, if applicable. IP will be administered by trained a licensed health care practitioner either at the research site or at a local clinic. At Visit 11 (Month 9) vitamin D and calcium will be provided.

Study Injections at a Local Clinic:

- Prior to receiving a romosozumab injection, the participant will send a photo to the study team of the pregnancy test results which must be negative.
- Local clinic will administer the injection and document details of the injection, vital signs, and any other pertinent information.
- The study team at the research site will be responsible for obtaining data on AEs, concomitant medications, questionnaires over the phone.

Visit 14 (Month 12):

VS will be obtained and AEs and concomitant medications recorded. Urine pregnancy test will be done, if applicable. DXA and CT of the hip and knee will be performed and blood obtained for serum bone markers. WISCI will be performed. Basic hematology, chemistry laboratory tests, and vitamin D levels will be assessed.

Alendronate, vitamin D and calcium will be dispensed with instructions for use. This will be the beginning of Year 2 and beginning of the treatment with alendronate.

STU00212405

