If individuals elect to withdraw from the study, a termination visit will be scheduled, if possible, at which time the reason for their discontinuation will be solicited to allow appropriate action. If withdrawal is due to medical reasons, related to the protocol, appropriate medical referral and follow-up will be recommended, which could include further safety visits until the event has passed. Participants may be withdrawn from the study by the principal investigator if in his judgment continuation in the protocol would be detrimental to the health or safety of the participant, if the participant is not compliant, or if funding no longer exists for the project.

Although every attempt will be made to retain subjects in this study, we do not plan to replace withdrawn subjects. If a participant withdraws from the interventional portion of a study and does not consent to continued follow-up of associated clinical outcome information, the investigator will not access the participant's medical record or other confidential records requiring the participant's consent for purposes related to the study. However, the investigator may review study data related to the participant collected prior to the participant's withdrawal from the study, and may consult public records, such as those establishing survival status.

STU00212405

Female subjects who become pregnant will be withdrawn from the protocol and will not be allowed to continue participation.

RISKS TO PARTICIPANTS

Romosozumab

Romosozumab may increase the risk of cardiovascular events of myocardial infarction, stroke and cardiovascular death. Therefore, romosozumab should not be initiated in patients who have had a myocardial infarction or stroke within the preceding year. Hypocalcemia and clinically significant hypersensitivity reactions including angioedema, erythema multiforme, dermatitis, rash, and urticaria have occurred in romosozumab-treated patients. Romosozumab is contraindicated in patients with uncorrected hypocalcemia and history of systemic hypersensitivity to romosozumab or to any component of the product formulation. Other potential risks include osteonecrosis of the jaw and atypical subtrochanteric and diaphyseal femoral fractures. These risks are rare and can occur spontaneously. The most common adverse events reported with the use of romosozumab includes: arthralgia, headache, muscle spasm, peripheral edema, asthenia, neck pain, insomnia, paresthesia, and injection-site reactions.

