APPENDIX A**Study Procedures Flowsheet**

Event	Screening	Baseline	Study Visits															
			0	Mo 1	Mo 2	Mo 3	Mo 4	Mo 5	Mo 6	Mo 7	Mo 8	Mo 9	Mo 10	Mo 11	Mo 12	Mo 15	Mo 18	Mo 24
Study Day	V1	V2	V3	V4	V5	V6	V7	V8	V9	V10	V11	V12	V13	V14	V15*	V16	V17	
Procedures:																		
Informed Consent	X																	
Demographic Data	X																	
Concomitant Medication	X	X	X	X	X	X	X	X	X	X	X	X	X	X	X	X	X	
Height	X																	
Weight	X																	
Vital Signs	X	X	X	X	X	X	X	X	X	X	X	X	X	X	X	X	X	
Medical History	X																	
Physical Exam	X																	
EKG	X																	
Urine pregnancy test	X	X	X	X	X	X	X	X	X	X	X	X	X	X	X	X	X	
Adverse Event Assessment		X	X	X	X	X	X	X	X	X	X	X	X	X	X	X	X	
Confirm Patient Meets Incl/Excl Criteria	X	X																
Administer/Dispense Study Drug	X	X	X	X	X	X	X	X	X	X	X	X	X	X	X	X	X	
Dispense Calcium/Vitamin D	X															X	X	X
Assess Compliance with calcium/vit D			X		X		X		X		X		X		X	X	X	X
WISCI	X	X														X		X
DXA Lumbar Spine (A-P View)	X															X		X
DXA Hip ROIs	X															X		X
CT Distal Femur/Proximal Tibia	X															X		X
CT Hip	X															X		X
Labs:																		
CBC	X															X		
Chemistry Panel/Serum Calcium	X		X													X		
FSH and Estradiol	X																	
TSH	X																	
25(OH) Vitamin D	X		X													X		
iPTH (I-84)	X																	
Urinalysis	X																	
Bone Markers		X			X				X			X			X		X	

*may be replaced with telephone call

**Serum Calcium and Vitamin D will be repeated at Mo 3 only if Mo 1 labs are abnormal.

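### A low Month 1 serum calcium is followed up only at Month 3 and is not linked to dosing, so the Month 2 injection is scheduled before any recheck

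*Combined protocol and SAP*

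**What the plan says.** All references are to the combined protocol and SAP.

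- **Procedures Involved, Visit 3 (Month 1).** Romosozumab is given, and serum calcium and vitamin D are checked. On an abnormal result: "If the results are abnormal, these labs will be repeated at Visit 5 (Mo 3".
- **Visit 4 (Month 2).** Vital signs, adverse events, concomitant medications and a pregnancy test where applicable, and then "IP will be administered by trained study staff". No calcium step is listed.
- **Visit 5 (Month 3).** An injection is listed, and also: "If serum calcium and/or vitamin D levels were abnormal at Month 1, participants will be retested at this visit".
- **Appendix A, footnote.** "Serum Calcium and Vitamin D will be repeated at Mo 3 only if Mo 1 labs are abnormal".
- **Risks to Participants, Romosozumab.** "Romosozumab is contraindicated in patients with uncorrected hypocalcemia".
- **Investigational Agents, Calcium.** "Because hypocalcemia can occur with treatment of osteoporosis, it is important for adequate calcium to be available". All participants are supplied calcium at 1000 mg/day. For those who already take calcium or get enough from diet, the study dose may be cut so that exogenous calcium stays within 1000 mg per day.
- **Withdrawal of Participants.** The principal investigator may withdraw someone "if in his judgment continuation in the protocol would be detrimental to the health or safety of the participant".

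**The concern.** The protocol recognises that calcium can fall on treatment, orders a test one month after the first dose, and names uncorrected hypocalcemia as a contraindication. It does not say what a low result means for the next injection. The only dated action is a repeat two months later, and staff may take that date as the required follow-up. A site that followed the visit list literally would inject at Month 2 without knowing whether the calcium had recovered.

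This is a matter of participant safety. It does not touch the sample size, the primary endpoint (distal femur vBMC at Month 12) or the planned Wilcoxon signed rank tests.

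**Working it through.** No formula or power figure is involved. The check is a trace of the schedule for a participant whose Month 1 calcium is low.

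| Visit | Romosozumab | Serum calcium | Stated link between result and dose |
|---|---|---|---|
| Screening | none | yes | normal value needed for entry, verified before the first dose |
| Baseline | yes | none | entry criteria checked |
| Month 1 | yes | yes | none; order of draw and dose not stated |
| Month 2 | yes | none | none |
| Month 3 | yes | only if Month 1 abnormal | none; result not required before dosing |
| Months 4-11 | yes | none | none |
| Month 12 | none (alendronate starts) | yes (chemistry panel) | none |

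**Counts**

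- Scheduled injections: baseline plus Months 1 to 11, so 1 + 11 = 12. After the Month 1 visit, 12 - 2 = 10 remain.
- Wait from the low value to the scheduled repeat: 3 - 1 = 2 months.
- Injections after the Month 1 visit and before the recheck visit: Month 2, so 1 of the remaining 10.
- Injections after the Month 1 visit and before the repeat result is known: Month 2 and possibly Month 3, so 1 or 2 of the remaining 10.
- The Month 1 injection is left out of these counts. It falls on the day of the draw, and the text does not say which comes first or whether the result is awaited.
- If the Month 3 repeat is still low, the next scheduled calcium is at Month 12, which is 12 - 3 = 9 months later, with the 8 injections of Months 4 to 11 in between. This gap matters only in that case.

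The protocol does say that bone marker blood is taken before the injection at follow-up visits in year 1, and Month 3 is a bone marker visit. The calcium sample may therefore be drawn before that dose, but this does not require its result to be back.

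**Other provisions that might supply the missing link**

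- Investigator discretion (Withdrawal of Participants) is removal from the study. It is not a temporary hold and sets no recheck.
- The treatment discontinuation rule in the section on monitoring safety needs a related serious adverse event. A low laboratory value need not be one.
- The pregnancy rule ("Female subjects who become pregnant will be withdrawn from the protocol and will not be allowed to continue participation") concerns a different condition.
- Supplements and entry criteria are preventive. They do not say what to do once a value is low.

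The protocol does write result-before-dose conditions elsewhere. A low screening vitamin D is repleted and redrawn before romosozumab starts, and participants of childbearing potential need a negative pregnancy test before injections. No such condition exists for on-treatment calcium.

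**The case against.** A reader might infer that the protocol contradicts itself, or that it instructs staff to dose a participant with known hypocalcemia. The documents do not support that. The contraindication is itself protocol text, and the retest rule says only when the blood is repeated. A clinician who sees a low value has a stated contraindication and stated authority to stop for safety. What is missing is an explicit link between result and dose. That part of the objection stands.

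The retest rule also covers any abnormal calcium or vitamin D result. For a high calcium, or an abnormal vitamin D alone, a Month 3 repeat is reasonable, so the point must be confined to low calcium.

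The risk is already reduced: normal calcium and vitamin D of at least 20 ng/ml at entry, exclusion of malabsorption and of creatinine clearance below 35 ml/min, supplements with compliance checks, adverse event review at the study visits, and an independent medical monitor. With 12 participants and no stated rate, a low Month 1 value may never occur. This limits the weight of the point, but none of these safeguards holds a dose or brings the recheck forward.

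Finally, the documents set the local laboratory normal range as an entry limit and give no threshold for later dosing. Using it as the hold limit is a choice. It has the merit of being already in the protocol, and the investigators could justify another.

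**Conclusion.** The point holds as a missing link between a safety result and the next dose. For a low Month 1 calcium, the only stated response is a repeat two months later. After the Month 1 visit, one scheduled injection precedes that recheck, and the Month 3 injection may precede its result. No dose hold, correction step or earlier recheck is stated.

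This rests on reading the visit descriptions and the Appendix A footnote as written, and it applies only to low calcium. It does not show that any participant would in fact be dosed while hypocalcemic, because the investigator may act on clinical judgement. The documents give no event rate, so no expected number of affected participants is claimed. No endpoint or analysis is affected. The amendment is worth making because the protocol names the contraindication itself and the remedy is cheap.

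**What to change.** Amend Visits 3 to 5 and the Appendix A footnote as follows.

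1. A Month 1 calcium below the local laboratory normal range is corrected and repeated before the Month 2 injection. Romosozumab is withheld until a normal result is available.
2. While calcium remains low, the same result-before-dose condition applies to every later injection, including any still outstanding after Month 3.
3. The condition extends to injections at local clinics (within Visits 9 to 13, Months 7 to 11). The clinics' listed duties do not include blood draws, so the text should say where the sample is taken and who releases the dose.
4. Corrective calcium may exceed the 1000 mg/day supplement limit in Investigational Agents.
5. A high calcium, or an abnormal vitamin D alone, keeps the Month 3 repeat.

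The cost is a few sentences of amendment and, for an affected participant, an occasional unscheduled blood draw or delayed dose. The draw is a real burden for non-ambulatory women, some of whom may live more than 100 miles away. A withheld dose also slightly reduces exposure before the Month 12 endpoint, so holds should be recorded. Because withdrawn participants are not replaced, a hold that can keep a participant in the study costs less than withdrawal.

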In man, treatment with antibody to sclerostin has been shown to result in significant increases in BMD in both post-menopausal women and men with OP. Specifically, romosozumab, a monoclonal antibody against sclerostin developed by Amgen, has not only shown increases in BMD but also reduction in fracture risk compared to both placebo and alendronate in randomized, controlled trials in post-menopausal women.[66, 67] In both trials, romosozumab was administered at a dose of 210 mg monthly for 12 months, followed by 12 months of either alendronate[67] or denosumab[66] treatment. Both BMD and fracture efficacy were evident after 12 months and maintained at 24 months. Compared to alendronate, both spine and hip BMD were greater at 12 months; and in a separate study, romosozumab treatment for 12 months resulted in greater increases in both spine and hip bone strength, determined by finite element modeling, than with teriparatide treatment.[68]

STUDY ENDPOINTS:

Primary Endpoint:

Change in integral vBMC at the knee (distal femur) at Month 12

Secondary Endpoints:

Change in DXA BMD at the total hip and femoral neck at Month 12

Change in vBMC at the hip at Month 12

Change in BMC/BMD at regions of interest around the knee at Month 12

Change in serum bone biomarkers at Month 12

Change will be assessed as both percent change from baseline and absolute change in all instances (see Statistical Analysis section below).

INVESTIGATIONAL AGENTS:

Romosozumab is a monoclonal antibody which inhibits sclerostin. It is marketed in the United States for the treatment of osteoporosis in post-menopausal women at high risk of fracture, defined as a history of osteoporotic fracture, or multiple risk factors for fracture; or who have failed or are intolerant to other available osteoporosis treatments. For this study, Amgen will provide romosozumab and a letter of cross-reference to their IND to satisfy CMC (Chemistry, Manufacturing, and Controls) and other documentation for FDA. Romosozumab will be stored in the locked and temperature-monitored refrigerator used solely for investigational drug products (IP) in our research space. The refrigerator is maintained in a locked room accessible only to research staff. All staff are required to sign in and sign out when opening the refrigerator, and a log is maintained of all activity. Dispensing of IP (both romosozumab and alendronate) is under the supervision of [name], PhD, principal investigator (PI) of this study.

STU00212405

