Visits 15 and 16 (Months 15 and 18):

VS will be obtained and AEs and concomitant medications recorded. Urine pregnancy test will be done, if applicable. Alendronate, vitamin D and calcium will be provided. Visit 15 (Month 15) may be completed over the phone with supplements mailed to participant's home, if needed.

Visit 17 (Month 24):

VS will be obtained and AEs and concomitant medications recorded. DXA and CT of the hip and knee will be performed and blood obtained for serum bone markers. Urine pregnancy test will be done, if applicable. WISCI will be performed.

Subjects who discontinue the study who have completed 6 months of treatment with romosozumab will be offered the opportunity to immediately enter into the alendronate phase of the study (months 12-24).

DATA OBTAINED:

Clinical and Demographic Information

Clinical and demographic information will be obtained by personal interview and, if necessary, review of medical records. This information will include a complete medical history, including demographic information, with specific emphasis on bone-related issues (history of fracture, endocrinopathy, vitamin D intake, etc.) utilizing a bone health questionnaire used by our group to acquire_baseline data for our in-house bone registry (Spinal Cord Injury & Lifestyle Information Form). They will also complete the Spinal Cord Independence Measure (SCIM) prior to initiating study drug. In order to assess ambulatory ability and status, participants will be asked to complete the Walking Index for Spinal Cord Injury II (WISCI) at each visit. This is a validated instrument to assess activity levels that affect bone loading and may be expected to have an impact on the effects of treatment that participants will be receiving.

DXA BMD

BMD will be determined by DXA at various skeletal sites: bilateral total hip, bilateral femoral neck, and spine. The DXA scans will be performed at Screening, 3 mos, 6 mos, 12 mos, and 24 mos by a trained DXA technician using a Hologic densitometer. Standard acquisition and analysis protocols will be used to quantify areal bone mineral density (aBMD) of all skeletal sites.

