We have had extensive experience in DXA imaging of individuals with SCI. There have been no technical problems with DXA imaging though positioning has been challenging for some participants due to contractures and spasticity, and orthopedic hardware has also prevented the full set of images from being obtained. As much as possible, positioning is reproduced at subsequent visits to allow appropriate comparisons.

CT determined bone parameters

CT imaging will permit determination of volumetric integral BMD at the knee (distal femur and proximal tibia) and hip as well as definition of compartmental BMC and BMD (trabecular and

STU00212405

cortical). The non-dominant knee and hip will be scanned (based on handedness), unless metal or other artifacts are present. We also have extensive experience in this technique, with >200 knees imaged and analyzed. The CT scans will be performed using a Siemens Somatom machine (120kVp, 280 mAs, pixel resolution 0.352 mm, slice thickness 1 mm). Each CT scan will include a phantom – placed on the side of, or underneath, the subject's knee (for knee scans) or hip (for hip scans) – with known calcium hydroxyapatite concentrations of 0, 0.4, and 0.8 g/cm³ (QRM, Moehrendorf, Germany). The phantom will serve as an interscan calibration, allowing for the conversion of CT Hounsfield units to bone equivalent density.

Three regions of bone will be analyzed corresponding to 0-10%, 10-20%, and 20-30% of segment length, as measured from the distal end of the femur or proximal end of the tibia. These regions were chosen based on their anatomical correspondence to epiphyseal (0-10%), metaphyseal (10-20%), and diaphyseal (20-30%) locations. The CT Hounsfield units will be converted to bone equivalent density and femora and tibiae will be segmented from CT images using a 0.15 g/cm³ threshold to identify the periosteal surface boundary. Methodology for CT measurement of the hip has been previously published.[69]

The CT scans will be performed at Baseline, 3 mos (knee only), 6 mos, 12 mos, and 24 mos.

Determinants of bone strength

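### Does the early-alendronate offer leave early switchers' Month 12 and Month 24 scans without a usable place in the analysis?

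*Combined protocol and SAP*

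**What the plan says.** PROCEDURES INVOLVED sets the planned course: romosozumab monthly for 12 months, "followed by 12 months of oral weekly alendronate 70 mg treatment". Visit 14 (Month 12) marks the change of drug: "This will be the beginning of Year 2 and beginning of the treatment with alendronate". At the end of Visit 17 the protocol adds an exception. It applies to "Subjects who discontinue the study who have completed 6 months of treatment with romosozumab". The exception is that these women "will be offered the opportunity to immediately enter into the alendronate phase of the study (months 12-24".

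The primary endpoint in STUDY ENDPOINTS is "Change in integral vBMC at the knee (distal femur) at Month 12". The section on CT-determined bone parameters fixes the imaging: "The CT scans will be performed at Baseline, 3 mos (knee only), 6 mos, 12 mos, and 24 mos".

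WITHDRAWAL OF PARTICIPANTS says that for women who choose to leave, "a termination visit will be scheduled, if possible, at which time the reason for their discontinuation will be solicited". It separately treats the woman who "withdraws from the interventional portion of a study and does not consent to continued follow-up", so it recognises that stopping treatment and leaving follow-up are different events. It also says that withdrawn women are not replaced. The section on monitoring participant safety encourages continued safety and imaging visits, directly after a sentence on stopping treatment for a related serious adverse event.

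STATISTICAL ANALYSIS AND SAMPLE SIZE DETERMINATION tests the absolute change between baseline and Month 12 with a Wilcoxon signed rank test in 12 women, and compares Month 24 with both earlier time points. It does not mention early switchers. Appendix A has no column for a termination or switch visit.

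**The concern.** Read word by word, the offer contradicts itself: a woman cannot leave the study and enter one of its phases, and a phase labelled months 12 to 24 cannot begin at month 6. If she really has left, she has no Month 12 scan. If she has not, her Month 12 scan reflects some alendronate as well as romosozumab, while the first objective concerns romosozumab alone. A third possibility is that her visits are re-dated to phase entry, so that an earlier scan stands in for Month 12.

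These readings can give different primary-endpoint values for the same woman. The study has 12 participants, no control arm, open-label treatment and no replacement. A choice made after the data are seen could therefore look selective.

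**Working it through.** **1. Do the sections conflict?**

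- *Planned course against the offer.* The 12-plus-12-month sequence and the Month 12 start of alendronate describe women who follow the plan. The Visit 17 sentence addresses those who do not. An exception that departs from the default does not contradict it, and the month label can be read as the name of the phase.
- *Withdrawal section against the offer.* The offer works only if discontinuing the study means stopping romosozumab. The withdrawal section already separates the interventional portion from follow-up, so this reading has a home in the protocol.
- *Safety section against the offer.* Encouraging imaging after treatment stops agrees with the offer. Even if it is limited to related serious adverse events, it conflicts with nothing.

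One loose phrase and one omission in the statistical section remain.

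**2. What do the scheduled scans contain for a switcher?** Count from first dose, with the switch at month *s* = 6 to 11.

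| Quantity | Formula | s=6 | 7 | 8 | 9 | 10 | 11 |
|---|---|---|---|---|---|---|---|
| Months of alendronate before Month 12 CT | 12 − s | 6 | 5 | 4 | 3 | 2 | 1 |
| End of alendronate, if the course is 12 months | s + 12 | 18 | 19 | 20 | 21 | 22 | 23 |
| Alendronate months between Months 12 and 24, same condition | (s + 12) − 12 | 6 | 7 | 8 | 9 | 10 | 11 |

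The last two rows hold only if her alendronate ends after 12 months. If it ran to Month 24, the whole 12-month interval would be on alendronate. The documents do not settle this, and I take no view on duration. Either way both CTs are on the schedule and each has a clear description.

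**3. What does the choice about the Month 12 pair cost?** The plan states 80% power at an effect size of 0.8, alpha 0.05 and n = 12. Simulating the exact signed-rank test with normal changes gives 0.801 one-sided and 0.669 two-sided, so the stated figure matches a one-sided test.

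- *Set the pair aside.* One-sided power is 0.748 at n = 11 and 0.706 at n = 10. Any lost pair costs this much, whatever the reason.
- *Keep the pair.* The value is the change at Month 12 in a woman who had 6 to 11 months of romosozumab and then 12 − s months of alendronate. The Background says that anti-resorptive drugs appear to prevent loss in SCI but have not been shown to raise bone mass. On that account the alendronate months would hold bone more than build it, so keeping her is more likely to understate a full-course effect than to create one. This is an inference; the documents give no figure for it.

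**The case for a change.** The strongest argument for a change is that the protocol itself creates this pathway, so it is more than a general question about dropouts. The rule could be written at no cost, and without it the decision might follow the result. It is true that the text is silent, that the wording is loose, and that a rule fixed beforehand is tidier.

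The argument weakens on size. A loss specific to this pathway can be calculated only by supposing that a scan taken at the switch is entered as Month 12 and that gain is linear over the year. The mean change is then understated by k × (1 − s/12)/12 for k switchers. At s = 6 that is 1 × 0.5/12 = 4.2% for one woman and 2 × 0.5/12 = 8.3% for two, and one-sided power moves from 0.801 to 0.768 or 0.731. No section says that such a scan counts as Month 12. Nor does the schedule list a CT at months 7 to 11, so only a month 6 switch would even have one. With visits counted from first dose these figures do not apply.

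The worry about selective choice is also limited. Few women could be affected, and the same Wilcoxon test with and without them shows at once whether the decision matters.

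**Conclusion.** No change follows. This is a gap that analysts fill sensibly: date visits from first dose, use the scans actually taken at Months 12 and 24, list any switchers with their months on each drug, and show the primary test with and without them. The planned endpoint, test and scan schedule all stay valid. The apparent contradictions reduce to a loose use of discontinuing the study and a phase label that was not written with switchers in mind.

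The size is nil if nobody switches. Otherwise each switcher brings one Month 12 value that includes 1 to 6 months of alendronate, or the loss of one of 12 pairs. This rests on two readings: that women who take the offer stop romosozumab but remain in follow-up, and that visits run from first dose. Both are the more natural readings, and no section contradicts them once the offer is taken as an exception. A woman who truly leaves has no Month 12 scan and is an ordinary missing value, which this offer did not create.
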